7.5.1 Seizure Classification and Diary

Each subject's seizure types will be documented on the Seizure Classification eCRF, according to clinical manifestation and the subject's own description. A study Investigator will then classify seizure types per the International League Against Epilepsy (ILAE) classification. Seizure classification will initially be conducted after consent, prior to submission to the Pre-Surgical Evaluation Committee for review, and then amended throughout the subject's participation in the study if new seizure types occur.

Subjects will be given paper-based seizure diaries to document occurrence of seizures after enrollment through study exit. The seizure diary will be initially provided to the subject after consent, prior to submission to the Pre-Surgical Evaluation Committee. Seizure types will be recorded for each subject in concordance with the initial Seizure Classification eCRF. Seizure diaries will be reviewed with the subjects and collected by the site at specified visits. The site will enter seizure information into the Seizure Diary Summary eCRF. Recorded data shall include qualifiers needed to determine Engel Classification per Appendix C (e.g., nocturnal seizures only or generalized convulsion with AED discontinuation). A new seizure diary may be issued to the subject at each visit if needed.

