7.19 Study Exit

A study exit eCRF is required for all subjects. Prior to exiting a subject from the study, it is recommended to follow the subject until all ongoing device-related, anesthesia-related, and/or procedure-related AEs are resolved or unresolved with no further actions planned. Upon exiting from the study, no further study data will be collected and no further study visits will occur for the subject. All data available through the time of the subject's exit will be used for analysis.

Subjects are urged to remain in the study as long as possible but may be exited from the study for any of the following situations:

- Subject has completed follow-up
- Subject lost to follow-up

- Subject death
- Subject did not meet inclusion/exclusion criteria (If ineligibility is discovered after the Visualase procedure, the subject will still be followed through 12 months post procedure.)
- Subject chooses to withdraw (e.g., consent withdrawal, relocation to another geographic location)
- Investigator deems withdrawal necessary (e.g., the subject enrolls in a confounding investigational study, the subject fails to maintain adequate study compliance, or it is medically necessary or in the best interest of the subject)

The following information is required to be documented at study exit:

- Reason for exit
- Date of study exit
- If the subject is determined to be lost to follow-up, details of a minimum of 3 contact attempts via 2 different methods (e.g., email, phone, and/or certified letter) must be recorded.

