7.1.3.2 Modified Intent to Treat (mITT) Population

All subjects who enter the operating room and start the Visualase procedure (i.e., undergo scalp incision) will be included in the mITT analysis population. The mITT population will be the primary analysis population for efficacy evaluations.

Non-compliance is defined as any subjects who have not submitted enough seizure diaries or qualifiers in their seizure diaries through 12 months, from which the Engel I Classification could not be determined at study exit because of the missing information. The detail of the seizure diaries refers to section 7.5.1 of CIP.

SLATE Statistical Analysis Plan Revision 1.0 Page 9 of 23 Medtronic

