7.4 Handling of Missing, Unused, and Spurious Data and Dropouts

7.4.1 Missing Data

Missing primary efficacy endpoint values and missing secondary endpoint values associated with testable hypotheses will be imputed for analysis with the mITT analysis population. Missing primary efficacy endpoint data will be imputed as a binary outcome of seizure freedom, regardless of missing pattern. No daily level imputation will be conducted.

The primary method of imputation will be multiple imputation (SAS PROC MI followed by MIANALIZE). Ten repetitions will be performed and, if needed, will be increased until the algorithm converges.

The Markov chain Monte Carlo (MCMC) method or Fully Conditional Specification (FCS) will be used with the default number of burn-in iterations before the imputation. The model variables will include: age, sex, race (white, African American, or other), and duration of disease.

SLATE Statistical Analysis Plan		Form
Revision 1.0	Page 10 of 23	Medtronic

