7.9.2 Primary Efficacy Endpoint

The primary efficacy endpoint is seizure freedom (defined as Engel Class I, Appendix 1) at 12 months following the Visualase procedure (starting at 30 days post-procedure through 365 days post-procedure, to align with Engel Class I definition).

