Appendix 1: Engel Classification of Postoperative Outcomeⁱ

Class I: Free of disabling seizures^a

- A. Completely seizure free since surgery
- B. Nondisabling simple partial seizures only since surgery
- C. Some disabling seizures after surgery, but free of disabling seizures for at least 2 years
- D. Generalized convulsions with AED discontinuation only

Class II: Rare disabling seizures ("almost seizure free")b

- A. Initially free of disabling seizures but has rare seizures now
- B. Rare disabling seizures since surgery
- C. More than rare disabling seizures since surgery, but rare seizures for the last 2 years
- D. Nocturnal seizures only

Class III: Worthwhile improvement^c

- A. Worthwhile seizure reduction
- B. Prolonged seizure-free intervals amounting to greater than half the followed-up period, but not <2 years

Class IV: No worthwhile improvement

- A. Significant seizure reduction
- B. No appreciable change
- C. Seizures worse

^aExcludes early postoperative seizures (first few weeks). This exclusion is quantitatively defined as 30 days for this protocol.

b"Rare" is quantitatively defined as ≤2 seizure days per year for this protocol.

^cDetermination of "worthwhile improvement" will require quantitative analysis of additional data such as percentage seizure reduction, cognitive function, and quality of life. This is defined as 80% reduction in seizures for this protocol.

Engel J. Outcome with respect to epileptic seizures. In *Surgical Treatment of the Epilepsies*, edited by J. Engel, Jr. Raven Press, New York. 1987

[figure not shown]
SLATE Statistical Analysis Plan		Form
Revision 1.0 Page 20 of 23		Medtronic

SLATE Statistical Analysis Plan Revision 1.0 Page 21 of 23 Medtronic

Revision 1.0

Page 22 of 23

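### SAP 7.4.1 imputes missing seizure freedom without the recorded seizure history and does not fix recorded failures first; the direction of bias depends on that rule and on who drops out

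*SAP*

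**What the plan says.** Protocol 14.9 makes multiple imputation with PROC MI the primary method for missing endpoints and leaves the predictors to the SAP. SAP 7.4.1 answers: "The model variables will include: age, sex, race (white, African American, or other), and duration of disease". It adds: "Missing primary efficacy endpoint data will be imputed as a binary outcome of seizure freedom, regardless of missing pattern", and "No daily level imputation will be conducted".

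The endpoint covers a window: "starting at 30 days post-procedure through 365 days post-procedure, to align with Engel Class I definition" (SAP 7.9.2). Seizure data accrue throughout that window. Protocol 7.5.1 states: "Subjects will be given paper-based seizure diaries to document occurrence of seizures after enrollment through study exit". The diaries are reviewed at 14 days and at 3, 6 and 12 months.

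Protocol 7.17 already counts retreatment and later open resection as failures of the primary endpoint. The only exception to imputation visible in SAP 7.4 is in 7.4.3: a subject whose death is judged seizure-related may not be imputed as seizure free.

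**The concern.** The chance of reaching day 365 seizure free rises with the time already spent seizure free. A model with four baseline variables cannot see this. It also cannot see that a subject had a disabling seizure in month 2 and so can no longer succeed at 12 months. Two things are therefore undefined or lost: whether a recorded failure stays a failure, and what is known about a subject who was still seizure free at last contact.

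The test is a comparison of a lower confidence limit with 43%, so a shift of one or two points in the estimate matters. A downward shift can cost a true success, and SAP 7.5 then stops all secondary testing. An upward shift raises the chance of a false success.

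**Working it through.** **Inputs from the documents.** 150 treated, expected rate 56%, threshold 43%, lower limit of a two-sided exact 95% interval, stated power 89% (SAP section 6); window of days 30–365 (SAP 7.9.2).

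**Assumptions.** The documents give no loss rate for the primary endpoint. I take 8, 15 or 23 of 150 lost (about 5–15%) and 50–70% of failures by day 180, spread evenly within days 30–180 and 180–365. The dropout hazard is constant from day 30, and the four baseline variables are uninformative. Seizures are known either to the day of loss or only to the last completed visit. Ten imputations are pooled by Rubin's rules with a t interval, because the visible SAP text does not say how an exact interval is pooled.

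**1. The plan's own figure.** The Clopper-Pearson lower limit is 42.39% at 76/150 and 43.05% at 77/150, so success needs 77. P(X ≥ 77) is 89.1% at a true 56%, which reproduces the stated 89%, and 2.4% at a true 43%.

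**2. What the model cannot see.** If F is the share of failures that occur by a given day, a subject seizure free to that day succeeds with probability 0.56/(1 − 0.44F).
- Day 31: F ≈ 0, giving 56%.
- Month 6: F = 0.5 to 0.7, giving 0.56/0.78 = 72% to 0.56/0.692 = 81%.
- Month 9 (day 270): F = 0.5 + 0.5 × 90/185 = 0.743, or 0.7 + 0.3 × 90/185 = 0.846, giving 83% to 89%.

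The named model imputes all of them at about 54–56%.

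**3. Recorded failures kept, dropout unrelated to outcome.** Only subjects lost while seizure free are imputed. Let m be their share of 150 and q their true success rate. Then 0.56 = (1 − m)·p + m·q, where p is the rate among known outcomes. The model imputes at p, so the estimate is p = (0.56 − mq)/(1 − m). With 15 lost, about 11–13 need imputation:
- Known to day of loss: m = 12/150, q = 0.72 gives 0.5024/0.92 = 54.6%; m = 11/150, q = 0.77 gives 0.5035/0.9267 = 54.3%.
- Known to last visit: m = 13/150, q = 0.65 gives 0.5037/0.9133 = 55.1%; m = 12/150, q = 0.70 gives 0.504/0.92 = 54.8%.

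Simulation agrees and supplies power:

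| Lost of 150 | Bias at true 56% (points) | Power |
|---|---|---|
| 0 | 0 | 89% |
| 8 | −0.4 to −1.0 | 82–86% |
| 15 | −0.8 to −1.6 | 76–81% |
| 23 | −1.4 to −2.6 | 67–76% |

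**4. Recorded failures kept, dropout three times as likely after a seizure.** If seizures are known to the day of loss, the estimate is about 55.5% with 8 lost and 55.0% with 15, a smaller downward bias. If they are known only to the last visit, it is about 55.4–56.3%, essentially unbiased, because unseen failures among the lost offset the model's error.

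**5. Recorded failures reset to missing.** If dropout is unrelated to outcome, false success at a true 43% is 2.3–2.9%, so there is no material inflation. If dropout is three times as likely after a seizure, the estimate at a true 56% is about 57–59%, and false success at a true 43% is about 4% with 8 lost and 6% with 15, against 2.4%.

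**6. Conditional imputation, recorded failures kept, dropout unrelated to outcome.** With 8, 15 and 23 lost, landmark imputation gives power of 86–88%, 83–86% and 78–86%. Its residual downward bias is 0.3–1.0 points if seizures are known to the day of loss and under about 0.1 if known to the last visit. Kaplan-Meier conditional imputation gives a mean of 56.0–56.1% and power of 88%, 87% and 85–88%.

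**The case against.** A reader might infer that the named model simply biases the seizure-free rate downward, against the device. The documents do not support that as a general statement. It needs a rule that the SAP does not state (recorded failures kept) and dropout unrelated to outcome; steps 4 and 5 show the bias shrinking, vanishing or reversing without them.

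The rule can be argued either way. For it: "All data available through the time of the subject's exit will be used for analysis" (Protocol 7.19). SAP 7.1.3.2 treats as non-compliant those subjects "from which the Engel I Classification could not be determined at study exit because of the missing information", and a disabling seizure in the window does determine the class unless Engel IB or ID applies. Class IC cannot rescue such a subject within 12 months, since it requires "Some disabling seizures after surgery, but free of disabling seizures for at least 2 years". Against it: the Protocol sentence is general, the SAP 7.1.3.2 sentence defines non-compliance rather than an imputation rule, and SAP 7.4.1 imputes whatever the missing pattern. The separate exception for seizure-related death would also be largely unnecessary if recorded seizures already fixed failure. I find the known-failure reading more natural, but it is not written down.

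The sizes are also open to challenge. Loss rates, seizure timing and the threefold ratio are all assumed. Late visits are analysed (Protocol 7.15) and telephone diary review is allowed (Protocol 7.15.5), so losses may be few; with 8 lost the effect is modest. SAP 7.4.2 is not visible, and the list of model variables may not be exhaustive. These points stand as limits. They do not remove the omission, because no visible text brings the seizure history in.

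**Conclusion.** The concern holds in this form: the named model leaves out recorded seizure history, and the visible text does not settle whether a recorded in-window seizure is a known failure. The direction of bias is not fixed. It is downward by about 0.4 to 2.6 points over 8 to 23 lost if recorded failures are kept and dropout is unrelated to outcome. It is smaller or about nil if they are kept and dropout follows seizures. It is upward if they are reset to missing and dropout follows seizures. All figures rest on the assumptions above. This should be fixed before database lock, with medium confidence in the size.

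Two further inferences go too far. One is that every death must count as a failure: that is a choice of estimand, not an error. The other is that imputation greatly inflates the spread of the cognitive and quality-of-life results. Secondary endpoints 3–7 are defined as within-subject change, so the natural reading is that the change is imputed, and the loss is then mainly precision.

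**What to change.** In SAP 7.4.1:

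- **(a)** State that a disabling seizure recorded in the day 30–365 window that does not qualify under Engel IB or ID is a known failure and is never imputed.
- **(b)** Together with (a), impute each subject lost while seizure free conditionally on being seizure free to last contact. The landmark form draws on subjects with known outcomes who were seizure free at the same last completed visit (3 or 6 months) and keeps the four baseline variables; a subject lost before the 3-month visit is imputed from all known outcomes. It stays within multiple imputation and yields one binary value per subject, so the exclusion of daily-level imputation still holds. Kaplan-Meier conditional imputation, with probability S(365)/S(day of last contact) and the curve re-estimated in a bootstrap sample for each imputation, is an alternative. It departs from the PROC MI method of Protocol 14.9, and that departure must be documented.
- Do not enter seizure-free days as a plain covariate in a model fitted to all subjects: every known success has 365 and every known failure fewer. Do not enter 3- or 6-month status that way either: under (a) an early seizure predicts failure perfectly.
- **(c)** For secondary endpoints 3–7, add the baseline and 6-month values of the same scale as predictors. The 6-month Rey test uses a different form, so it serves as a predictor only.

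In SAP 7.4.3, state that the seizure-related-death exception also applies to secondary endpoints 1, 2 and 8, which SAP 7.5 describes as analyses of the primary endpoint.

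The cost is SAP wording and slightly more analysis work, with no new visits or subjects. The landmark form leaves the small residual bias shown in step 6. Conditional imputation also assumes that unrecorded seizures after last contact do not drive the loss; if they do, it errs upward, so seizure status at last contact should be captured as fully as possible.

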14.3.2 Modified Intent to Treat (mITT) Population

All subjects who enter the operating room and start the Visualase procedure (i.e., undergo scalp incision) will be included in the mITT analysis population. The mITT population will be the primary analysis population for efficacy evaluations. Missing primary and secondary efficacy endpoints that are testable will be imputed. Imputation for the specified secondary cognitive and QOL efficacy endpoints will only include the English language version subset.

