14.9 Missing Data

Missing primary efficacy endpoint values and missing secondary endpoint values associated with testable hypotheses will be imputed for analysis with the mITT analysis population. The primary method of imputation will be by multiple imputation (SAS PROC MI and MIANALIZE) using the Markov chain Monte Carlo method. Details of predictor variables to be used in SAS PROC MI, seed number, and number of imputations to be performed will be provided in the SAP.

14.10

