The primary efficacy endpoint is the 12-month seizure-free rate. The analysis of the primary efficacy endpoint will compare the lower 2-sided exact 95% confidence interval (CI) boundary of the observed rate against 43%. The lower bound of the seizure freedom rate CI following the Visualase procedure must exceed 43%. Based on published and unpublished accounts of seizure freedom rates following laser ablation for MTLE, it is expected that approximately 56% of subjects who undergo the Visualase procedure will be seizure free through 12 months post-procedure. Given the assumption of a 56% success rate with Visualase, 89% power can be achieved with 150 treated subjects to show that the success rate after Visualase is superior to 43%.

Subjects will be considered enrolled upon the signing of a consent form. It is anticipated that once enrolled, some subjects will not proceed to the Visualase procedure due to failure at their pre-surgical evaluation, changes in clinical status, or non-compliance to protocol. Based on these factors, and on previous reports of attrition in similar studies, the assumed attrition rate is 30%. To account for this attrition, up to 215 subjects may be enrolled to ensure at least 150 subjects are treated with the Visualase procedure.

Certain secondary endpoint assessments will be made using subject questionnaires. These self-reported instruments are influenced by primary language. Validated translations are not available in all languages; thus, enrollment will be limited to subjects who can complete these assessments in either English or Spanish. Further, the impact of grouping across translations for analysis is an important consideration. Therefore, for the specified secondary cognitive and QOL endpoints, the subset of only the English-language versions will be used for analysis. To preserve adequate statistical power for analysis of this subset, the total Spanish language enrollment will be restricted to no more than 40% of the total study-wide enrollment population. A 40% cap was chosen based on a conservative assumption that only 73% of subject data are usable, resulting in an evaluable sample of N=109. If only 50% of this sample were used for secondary endpoints restricted to English language (N=55), the power to detect a change in the neuropsychological assessments would be 86%, based on best-estimate effect size.

7. General Statistical Considerations

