7.9.3.3 Secondary Endpoint #3

Within-subject change of Boston Naming Test score (English language version), from baseline to 12 months following the Visualase procedure

It is hypothesized that the Boston Naming Test score will not decrease from baseline to 12 months following the Visualase procedure. The hypotheses associated with this endpoint are as follows:

Null Hypothesis: μ (V-BNT - BSL-BNT) + $\delta \le 0$ Alternate Hypothesis: μ (V-BNT - BSL-BNT) + $\delta > 0$

Where μ (V-BNT - BSL-BNT) = mean difference in the Boston Naming Test score from baseline to Month 12 post Visualase.

A non-inferiority test will be performed using a paired t-test, with a non-inferiority delta (δ) of one Reliable Change Index (RCI) of 5 points, to test the hypothesis of no reduction. The 5-point RCI is based on published literature (Sawrie 1996). A two-tailed alpha of 0.05 will be used.

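### The imputation variables listed for secondary endpoints 3–7 omit each subject's baseline and 6-month score on the same test, and the SAP does not say whether the 12-month score or the change is imputed

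*SAP*

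**What the plan says.** SAP 7.4.1 sets the scope: "Missing primary efficacy endpoint values and missing secondary endpoint values associated with testable hypotheses will be imputed for analysis with the mITT analysis population". Endpoints 3–7 all carry hypotheses, so they are covered. On method it says "The Markov chain Monte Carlo (MCMC) method or Fully Conditional Specification (FCS) will be used", and on number "Ten repetitions will be performed and, if needed, will be increased until the algorithm converges". The only predictors it names are in "The model variables will include: age, sex, race (white, African American, or other), and duration of disease". Protocol 14.9 defers to the SAP here: "Details of predictor variables to be used in SAS PROC MI, seed number, and number of imputations to be performed will be provided" in that document. Protocol 14.3.2 adds only a restriction on who is included: "Imputation for the specified secondary cognitive and QOL efficacy endpoints will only include the English language version subset".

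Endpoints 3–7 are within-subject changes. Endpoint 3 (SAP 7.9.3.3), for example, tests the "mean difference in the Boston Naming Test score from baseline to Month 12 post Visualase" with a paired t-test against a 5-point margin. Endpoint 4 does the same for the RAVLT with a 15-point margin. Endpoints 5–7 apply sign tests to change categorised at a minimal important difference.

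The Schedule of Events (Protocol Table 2) has all of these instruments given at baseline, 6 months and 12 months. The RAVLT uses Form A at baseline and 12 months and Form GE-AB at 6 months.

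**The concern.** Baseline is part of the endpoint, and the 6-month score is likely to be the closest available predictor of the 12-month score. An imputation model without them cannot use what is known about a subject who drops out after a low baseline or an early decline. The missing-at-random assumption then has to hold given age, sex, race and disease duration alone.

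Two things are at stake. The estimated change may be shifted, and for the non-inferiority tests a shift towards improvement makes a false pass more likely. Precision may also be lost without need. Testing stops at the first failure (SAP 7.5, 7.9.3), so endpoints 3 and 4 decide whether endpoints 5–8 are tested at all.

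**Working it through.** **The plan's own figures.** The primary sample size reproduces. With 150 subjects, the exact lower limit exceeds 43% from 77 successes upward, and power at 56% is 0.891 (stated: 89%). This does not depend on the present point. SAP Section 6 assumes that "only 73% of subject data are usable": 150 × 0.73 = 109.5 (stated N=109), and half of 109 is 54.5 (stated N=55). The 86% power at N=55 cannot be checked, because no effect size is given.

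**Assumed inputs, not in the documents.** n = 90 English-language subjects (60% of 150), SD σ = 8 at each visit, and correlations baseline/12-month 0.75, baseline/6-month 0.80 and 6-month/12-month 0.85. The listed demographics are taken as nearly unrelated to score. The missing fraction p = 0.27 is borrowed from 1 − 0.73, so 65.7 subjects are observed and 24.3 missing.

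**1. Completely random loss.** The observed mean estimates the right quantity on either reading, so the mean change is unbiased. For the standard error, use Rubin's rules with 10 imputations: T = W + 1.1 × B.

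- Variance of a true change: 2 × (1 − 0.75) × 64 = 32. Variance of a change with an unrelated imputed score: 2 × 64 = 128.
- *Score imputed without baseline:* W = (0.73 × 32 + 0.27 × 128)/90 = 0.644; B = 0.27² × (64/65.7 + 64/24.3) = 0.263; SE = √(0.644 + 0.289) = 0.97. The actual spread of the estimate is √(64/65.7 + 64/90 − 2 × 0.75 × 64/90) = 0.79. The reported SE is therefore too large, which is conservative.
- *Change imputed:* W = 32/90 = 0.356; B = 0.27² × (32/65.7 + 32/24.3) = 0.132; SE = √(0.356 + 0.145) = 0.71. This is valid.
- *Baseline and 6-month score in the model:* R² = (0.75² + 0.85² − 2 × 0.75 × 0.85 × 0.80)/(1 − 0.80²) = 0.736; residual variance 64 × 0.264 = 16.9; B = 0.27² × (16.9/65.7 + 16.9/24.3) = 0.069; SE = √(0.356 + 0.076) = 0.66.

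Simulation agrees: 0.96 for the score without baseline and 0.66–0.67 with own scores. At a true loss of 2.5 points against the 5-point margin, simulated power is 75–76% and 96–97% respectively. In a second set of simulations (SD 1, baseline/12-month correlation 0.6 or 0.8), imputing the change cost 2–3% in SE at 10% missing and 6–7% at 27%.

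**2. Loss related to low baseline.** Let d be the baseline gap in points, retained minus lost.

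- Score imputed: bias = p × 0.75 × d = 0.2025 × d, towards improvement.
- Change imputed: bias = p × (0.75 − 1) × d = −0.0675 × d, towards worsening.

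Simulations with a true change of −5.0 gave −4.3 to −3.7 when the score was imputed, depending on how strong the mechanism was made. By the first formula these correspond to gaps of 0.7/0.2025 = 3.5 and 1.3/0.2025 = 6.4 points. False non-inferiority was 7% and 13% in two of these runs, against about 2.5% with own scores added. Imputing the change gave −5.4 in one run, which is against the device.

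**3. Loss related to early decline.** Let g be the gap in 6-month change, retained minus lost. The regression slope of 12-month change on 6-month change is (0.85 − 0.75 − 0.80 + 1)/(2 × (1 − 0.80)) = 0.30/0.40 = 0.75. If the change is imputed, bias = 0.27 × 0.75 × g = 0.2025 × g, towards improvement. A simulated estimate of −4.1 against −5.0 corresponds to g = 0.9/0.2025 = 4.4 points. False-pass rates ran from about 10% to about 25%, the latter under a deliberately strong mechanism.

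**4. After the fix.** In the second set of simulations, with both earlier scores in the model, bias was at most 0.01 SD and coverage 94–97% in every scenario. Baseline alone was not enough when loss depended on the 6-month score: bias of 0.03–0.08 SD remained.

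**The case against.** The strongest reply has four parts.

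- **The natural reading is that the change is imputed.** The SAP imputes endpoint values, endpoints 3–7 are defined as changes, and the primary endpoint is imputed at the derived level. On that reading the pairing is kept, and random loss costs only a few percent in SE. Loss on a low 6-month level is then nearly harmless (bias 0.01–0.02 SD, coverage 94–95%), and loss on low baseline works against the device. This stands as far as it goes. It does not cover loss related to early decline, and the SAP does not settle the reading.
- **The list may be open.** It says what the model will include, and it does not name the variable being imputed. Baseline and 12-month scores entered jointly would preserve the pairing. The public text passes from 7.4.1 to 7.4.3, so further detail in 7.4.2 cannot be excluded. This is fair. But Protocol 14.9 assigns the predictors to the SAP, and no available text names the earlier scores.
- **The sizes are assumed.** This stands. The 73% is a conservative planning figure used to justify the Spanish-language cap, not a forecast of missing 12-month scores.
- **The RAVLT form differs at 6 months.** This is true, but an alternate-form score can still serve as a predictor.

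A reader might also infer that every missing 12-month score yields a wrong change and a wrong standard error even under random loss. The documents do not support that. Under random loss the mean is unbiased on either reading, and the SE is wrong only if the score is imputed without baseline, in which case it is too large.

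**Conclusion.** The point holds as a free improvement. The listed imputation variables omit the same-test baseline and 6-month scores for endpoints 3–7, and the imputed quantity is not stated.

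- **Loss related to earlier scores:** the change is biased. Imputing the score errs towards improvement when low-baseline subjects are lost. Imputing the change errs towards improvement when early decliners are lost, and towards worsening when low-baseline subjects are lost.
- **Completely random loss:** no bias. Imputing the score without baseline inflates the SE (0.96 against 0.66–0.67, power about 75% against 95–97% in the one scenario worked). Imputing the change is valid and slightly less precise.

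These sizes depend on the assumed SD, correlations, missing fraction and loss mechanisms. Nothing has been sized for the 15-point RAVLT margin or for the sign tests at their stated cut-points. The documents do not show that loss will in fact depend on earlier scores. The primary efficacy endpoint's stated power is unaffected.

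**What to change.** In SAP 7.4.1, for each of endpoints 3–7:

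- add the baseline and 6-month score of the same test to the imputation model, noting that the 6-month RAVLT score comes from Form GE-AB;
- state that the 12-month score is imputed, with the change and (for endpoints 5–7) its MCID category derived afterwards in each completed data set;
- keep age, sex, race and duration of disease.

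This is one or two sentences, to be settled before database lock. All the variables are already collected, so there is no added burden on subjects or sites.
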